#### **10.2.5 Laboratory Test Abnormalities**

Laboratory test results will be maintained at the site and must be reviewed and signed by the Investigator or Sub-Investigator. Laboratory test value abnormalities should not be reported on the AE page of the CRF as AEs unless they indicate a clinically relevant condition.

#### **10.2.6 Physical Examination**

A complete physical examination will include body weight and the examination of the following body systems: general appearance, skin, HEENT (head, ears, eyes, nose, throat), cardiovascular, pulmonary, abdomen, neurological, lymph nodes, spine, and extremities (skeletal). Height will be measured at screening only.

Any abnormalities will be recorded on the CRF. Information about the physical examination must be present in the source documentation at the study site. Significant findings that are present before the start of the study must be included in the Relevant Medical History/Current Medical Conditions

CRF. Significant findings made after the start of study drug that meet the definition of an AE must be recorded on the AE CRF.

### **10.2.7 Vital Signs**

Vital signs, including blood pressure, heart rate and body temperature, will be measured using clinically acceptable methods and devices at each clinic visit. Blood pressure should be recorded with the patient seated (all visits) **or** supine (all visits).

Any patient with vital signs outside of the acceptable range (blood pressure between 100 and 140 mmHg systolic and 60 and 90 mmHg diastolic; heart rate between 60 and 99 beats/minute) will have his/her vital signs repeated within 15 minutes. If the repeat measurement remains outside of the acceptable range, the Principal Investigator or Sub-Investigator will determine the course of action. An AE will be reported for the out-of-range measurements if deemed clinically significant.

### **10.2.8 Biochemistry / Hematology**

Blood samples will be collected for the purposes of determining a patient's eligibility as indicated in the Schedule of Study Activities (**Table 3-1**). The Screening laboratory tests include a basic metabolic profile and CBC. Samples will be analyzed at local laboratories using the laboratory's normal ranges. The local laboratory procedures and normal ranges will be collected from the site prior to beginning enrollment. Each patient sample will be analyzed to provide the result for each parameter.

Laboratory tests included are listed below.

**CBC:** Hemoglobin, hematocrit, white blood cell (WBC) count, red blood cell (RBC) count, platelet count, mean corpuscular volume (MCV), mean corpuscular hemoglobin (MCH), mean corpuscular hemoglobin concentration (MCHC), red cell distribution width (RDW), and mean platelet volume (MPV).

**Basic Metabolic Profile:** Glucose, calcium, sodium, potassium, CO2, chloride, blood urea nitrogen (BUN), creatinine, and calculated eGFR.

If any laboratory result is in question, it will be repeated. It is the Investigator's responsibility to review the results of all lab tests once available. For each lab value outside the normal range, the Investigator is to determine if this is a clinically significant change from baseline for that patient. An AE will be reported for the out-of-range measurements if deemed clinically significant or requires therapy. Repeat lab tests of additional tests to verify original lab results may be needed.

### **10.2.9 Study Drug Dose and Monitoring of Whole Blood Trough Level for Tacrolimus**

The dose of TAC-IR or ENVARSUS XR being administered to the patient will be recorded on the appropriate CRF.

Whole blood, for the purpose of tacrolimus trough level measurement, will be drawn at the designated time points listed in the Study Schedule and analyzed at the local laboratory. The local laboratory procedure for tacrolimus trough level measurement will be collected from each site prior to enrollment.

#### **10.2.10 Concomitant Medications**

All current concomitant medication will be recorded and documented for dose, brand name and/or generic name. The reason for any change in the dose or choice of concomitant immunosuppressant medication will also be recorded on the appropriate CRF.

### **11 SAFETY MONITORING**

Routine safety assessments will consist of monitoring and recording all AEs, including SAEs, the regular monitoring of vital signs and physical condition as described in [Section 10](#).

#### **11.1 Warnings and Precautions**

ENVARSUS XR tablets are an extended-release formulation of tacrolimus, intended for once daily oral administration. Refer to the ENVARSUS XR Full Prescribing Information for detailed description of the warnings and precautions associated with this formulation of tacrolimus.

#### **11.2 Pregnancies**

Any pregnancy that occurs during study participation should be reported using a Pregnancy Form. The pregnancy should be followed up to determine outcome, including spontaneous or voluntary termination, details of birth, and the presence or absence of any birth defects, congenital abnormalities, or maternal and newborn complications. For additional instructions for rapid notification of pregnancies please see [Section 16.1.2](#).

## **12 PROTOCOL AMENDMENTS, OTHER CHANGES IN STUDY CONDUCT**

### **12.1 Protocol Amendments**

Any substantial changes will be made as formal amendments to the protocol and will be submitted to the local IRB for appropriate review and approval, and to regulatory authorities.

### **12.2 Other Changes in Study Conduct**

Material changes in study conduct as defined in this protocol are not permitted.

Any unforeseen changes in study conduct will be recorded in the case report forms.

## **13 DATA MANAGEMENT**

### **13.1 Data Recording and Documentation**

Data collection will involve the use of source documents and REDCap, to which only authorized personnel will have access.

All data collected in the context of this study will be stored and evaluated per regulatory requirements and applicable guidance for electronic records. All electronic record systems will be fully qualified and validated for the intended use per the International Society of Pharmaceutical Engineers (ISPE) Good Automated Manufacturing Practice (GAMP®) guidelines, 21 Code of Federal Regulations (CFR) Part 11 (FDA regulation for Electronic Records and Electronic Signatures) and the International Conference on Harmonization (ICH) Guidance on Good Clinical Practice (ICH E6).

Also, data will be stored and evaluated in such a way as to guarantee patient confidentiality in accordance with the legal stipulations applying to confidentiality of data. Study records (e.g., copies of CRFs, regulatory documents) will be retained at the study center, along with adequate source documentation, according to FDA and International Conference on Harmonization of Technical Requirements for Registration of Pharmaceuticals for Human Use requirements. All study records must be available for inspection by Sponsor, its authorized representatives, the FDA, and other regulatory authorities.

### **13.2 Database Management and Quality Control**

Data items from the source documents will be entered into the REDCap.

## **14 STATISTICAL METHODS**

All analyses will be performed using SAS® for Windows statistical software (SAS Institute, Cary, NC) using validated implementations of each application or SAS custom programming. Programs, logs, and output will be reviewed for accuracy according to relevant Standard Operating Procedures (SOPs). A full Statistical Analysis Plan will be developed and finalized prior to data base lock. The plan will include a thorough description of the statistical methods to be used to address study objectives.

In general, continuous variables will be summarized with number of non-missing observations, mean, standard deviation (SD), median, minimum, and maximum displayed. Categorical variables will be summarized as counts and percentages.

## 14.1 Sample Size

The study aims to enroll approximately 60 patients. With an expected drop-out rate of 10% to 15%, a maximum of fifty-two (52) evaluable patients are expected to reach the end of study.

In order to detect an effect size of 0.5 with 80% power and a one-sided type I error rate of 0.025, a sample size of 34 evaluable patients is needed. (NOTE: We simply need at least 34 patients to have adequate power, but we anticipate approximately having 52, meaning that this study will almost certainly NOT be underpowered). An interim analysis will be conducted when data are available for 17 (half of 34) evaluable patients, to better estimate the variation and effect of the treatment.

The rule for sample size adjustment is as follows:

Denote the planned sample size  $(n) = n_1 + n_2$ , where  $n_1 = 17$ ; and  $n = 34$  (i.e.,  $n_2 = 17$ ) Let

$r=1.5$  be the rate of adjustment (which leads to the maximum sample size of 52). Define

$N_{\text{new}}$  (final sample size) as

$$N_{\text{new}} = \begin{cases} n_1 + K, & n \leq N \leq rn \\ n, & N < n \\ rn, & N > rn \end{cases}$$

where  $K$  is the calculated additional required sample size (beyond first 17 evaluable patients) and  $N$  is the calculated total required sample size based on the observed change and variation from the interim analysis.

The range of possible total sample sizes based on the interim analysis is from 34 and 52, i.e., the sample size remains at 34 if the adjusted estimate is below 34, and increases to a maximum of 52 if the adjusted estimate is beyond 52.

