### **Sample Size Considerations:**

The study aims to enroll approximately 60 patients. With an expected drop-out rate of 10% to 15%, a maximum of fifty-two (52) evaluable patients are expected to reach the end of study.

In order to detect an effect size of 0.5 with 80% power and a one-sided type I error rate of 0.025, a sample size of 34 evaluable patients is needed. (NOTE: We simply need at least 34 patients to have adequate power, but we anticipate approximately having 52, meaning that this study will almost certainly NOT be underpowered). An interim analysis will be conducted when data are available for 17 (half of 34) evaluable patients, to better estimate the variation and effect of the treatment.

The rule for sample size adjustment is as follows:

Denote the planned sample size  $(n) = n_1 + n_2$ , where  $n_1 = 17$ ; and  $n = 34$  (i.e.,  $n_2 = 17$ )

Let  $r=1.5$  be the rate of adjustment (which leads to the maximum sample size of 52). Define  $N_{\text{new}}$  (final sample size) as

$$N_{\text{new}} = \begin{cases} n_1 + K, & n \leq N \leq rn \\ n, & N < n \\ rn, & N > rn \end{cases}$$

where  $K$  is the calculated additional required sample size (beyond first 17 evaluable patients) and  $N$  is the calculated total required sample size based on the observed change and variation from the interim analysis.

The range of possible total sample sizes based on the interim analysis is from 34 and 52, i.e., the sample size remains at 34 if the adjusted estimate is below 34 and increases to a maximum of 52 if the adjusted estimate is beyond 52.

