**Analysis Methods:**

In general, continuous variables will be summarized with number of non-missing observations, mean, standard deviation (SD), median, minimum, and maximum displayed. Categorical variables will be summarized as counts and percentages.

The primary efficacy endpoint is the Global Composite Score on the RBANS. Raw scores on the RBANS will be age adjusted and converted into a series of Index Scores (reflecting domains such as immediate memory, delayed memory, attention, etc.) which will in turn be combined to generate the aforementioned Global Composite Score, a summary score reflective of overall neuropsychological status (scores have a mean of 100, SD of 15, impairment is typically defined as a score of <78 (1.5 SD below the mean). Descriptive summaries of patients' scores and percentiles at baseline (i.e., Visit 2) and post-baseline (i.e., Visit 3) will be provided. The mean change (absolute change) in -score the RBANS composite score from baseline to post-baseline will be evaluated using paired t-test at 0.05 significance level. A 95% confidence interval (CI) will be constructed for the mean change. Same methods will be used to analyze other cognitive test scores.

CGI-I and PGI-I will be summarized by number and percentages of patients in each category as well as combined categories of improvement (e.g., "Minimum improved", "Much improved", "Very much improved [CGI-I]/Very much better [PGI-I]").

Safety analyses (i.e., ENVARSUS XR exposure, adverse events, and trough level of ENVARSUS XR), as well as vital signs will be summarized descriptively.

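### The re-estimation formula caps the final sample size at 51, but the text beside it says 52, in both Section 14.1 and the synopsis

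*Combined protocol and SAP*

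**What the plan says.** Section 14.1 (Sample Size) and the synopsis (Sample Size Considerations) carry the same rule.

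- **Planned size.** The plan holds that "a sample size of 34 evaluable patients is needed" for a standardised effect of 0.5, with power of 80% and one-sided alpha of 0.025.
- **Interim.** "An interim analysis will be conducted when data are available for 17 (half of 34) evaluable patients". From it a required total N is calculated.
- **Formula.** With n = 34 and r = 1.5, the final size is n if N < n, the first 17 patients plus the calculated addition if N lies between n and rn, and rn if N > rn.
- **Text around the formula.** The value r = 1.5 is said to "be the rate of adjustment (which leads to the maximum sample size of 52". The closing sentence opens with "The range of possible total sample sizes based on the interim analysis is from 34 and 52" and ends by saying that the size "increases to a maximum of 52 if the adjusted estimate is beyond 52".
- **A second use of 52.** From approximately 60 enrolled and 10% to 15% drop-out, "a maximum of fifty-two (52) evaluable patients are expected to reach the end of study".

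**The concern.** The cap is one of the thresholds of an adaptive rule. The third branch of the formula yields 1.5 × 34, and the surrounding sentences give a different number for the same quantity. Anyone applying the rule after the interim would have to depart from either the formula or the text, and would be choosing after interim data had been seen. A pre-specified rule should give one answer for each interim result. What is at stake is the clarity of the rule. The two answers differ by a single patient.

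**Working it through.** **Inputs.** From Section 14.1: effect size 0.5, power 80%, one-sided 0.025, n = 34, n1 = 17, r = 1.5, approximately 60 enrolled, 10% to 15% drop-out. From the synopsis (Analysis Methods), the mean change is "evaluated using paired t-test at 0.05 significance level"; read as two-sided, this matches the one-sided 0.025.

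**1. Planned size.** Paired t-test power from the noncentral t distribution, with n − 1 degrees of freedom and noncentrality 0.5 × √n: 79.5% at n = 33 and 80.8% at n = 34. The plan's 34 is reproduced.

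**2. The cap.** rn = 1.5 × 34 = 51, an integer, so rounding is not involved. A cap of 52 would need r = 52/34 = 1.529, or n = 52/1.5 = 34.67. Two other routes also miss 52:
- 1.5 times the unrounded n of 33.37 gives 50.05.
- n1 + 1.5 × n2 = 17 + 25.5 = 42.5.

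**3. Formula against text.**

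| Interim N | Final size by formula | Final size by text |
|---|---|---|
| 30 | 34 | 34 |
| 40 | 40 | 40 |
| 51 | 51 | 51 |
| 52 | 51 | 52 |
| 60 | 51 | 52 |
| 100 | 51 | 52 |

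The two agree up to 51 and differ by one for every larger N.

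**4. How often the branch is reached.** The plan gives no formula for N. Assume N = ((1.960 + 0.842)/d1)², where d1 is the observed mean change divided by its SD in the 17 interim patients. Then N > 51 when d1 is below 2.802/√51 = 0.392, that is, when the interim t statistic is below 0.392 × √17 = 1.617. With 16 degrees of freedom and noncentrality (true effect) × √17, and with results in the wrong direction also sent to the cap:
- true effect 0.5: 32.6%
- true effect 0.4: 47.8%
- true effect 0: 93.7%

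Simulation of 200,000 trials per effect size gives 32.5%, 47.6% and 93.7%. The treatment of wrong-direction results matters only near zero effect. If d1 is simply squared, so that a large worsening counts as needing few patients, the figure at zero is 87.5%, while at 0.5 and 0.4 it is 32.5% and 47.7%.

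**5. What one patient is worth.**

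| Quantity | 51 patients | 52 patients | Difference |
|---|---|---|---|
| Power at effect 0.5 | 93.84% | 94.26% | 0.4 points |
| Power at effect 0.4 | 79.99% | 80.78% | 0.8 points |
| Effect detectable with 80% power | 0.400 | 0.396 | 0.004 |

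**6. The other 52.** 60 × 0.90 = 54 and 60 × 0.85 = 51. So 52 lies inside the range and is not its maximum; it corresponds to a drop-out of 8/60 = 13.3%.

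**The case against.** The strongest reply is that this hardly matters. The study is declared exploratory. Section 10.1.6 says withdrawals are not replaced, and evaluability depends partly on Visit 3 data, so the final evaluable count cannot be steered to within one patient. A reply of this kind would add that 52 is printed as the cap three times in each place and 51 never, so 52 may be what was intended, with 1.5 a rounded rate. Both points stand. They limit the weight of the issue and leave the choice of number to the sponsor. They do not make the formula and the text agree.

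Four stronger readings are tempting, and the documents do not support them.

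- **A reader might infer that 52 cannot be reached.** Enrolment is only approximately 60, and 52 needs a drop-out of 13.3%, within the plan's range. Even at 15%, 52/0.85 = 61.2, so 62 enrolled would be enough. A cap is also a ceiling, not a number that has to be attained.
- **A reader might infer that 51 to 54 should replace 52 as the expected number.** Those are completers. The Evaluable Dataset in Section 14.2 also requires a trough of 3-9 ng/mL, cognitive data before and after conversion, and no major deviation affecting the measurement. The upper figure would be more optimistic than the present one.
- **A reader might infer a threat to the type I error.** Section 14.7 leaves the final test unadjusted for the interim look, but that is a separate matter, which moving the cap by one patient does not change. No inflation from the one-patient ambiguity has been shown.
- **A reader might take the frequencies in step 4 as properties of the plan.** They depend on an assumed formula for N. Section 14.7 also bases the interim on CPT-III omission measures, so they cannot be tied directly to the effect of 0.5 assumed for the RBANS endpoint.

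**Conclusion.** The inconsistency is real and follows from the plan's own numbers without any assumption: the formula caps the size at 51 and the text caps it at 52, in both Section 14.1 and the synopsis. It affects every interim N above 51. Under the normal-approximation assumption for N, that is about one trial in three at a true effect of 0.5 and nearly half at 0.4. Its effect is one patient and 0.4 to 0.8 points of power. It is a minor wording correction to a pre-specified rule. The base size of 34 is sound, and neither the adequacy of the trial nor its conclusions are at risk. The word maximum attached to the 52 evaluable patients is a separate small slip.

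**What to change.** Before the interim analysis, make the formula and the text agree on one cap in Section 14.1 and in the synopsis. The simplest way is to replace 52 by 51 in the three re-estimation statements: the clause attached to r, the range of possible sizes, and both mentions in the closing sentence. This keeps r = 1.5 and the formula as they are. The equivalent alternative is to keep 52 and define r as 52/34 (about 1.53).

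Separately, describe 52 evaluable patients as an approximate expectation instead of a maximum, and do not put 51 to 54 in its place.

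The cost is a wording amendment. If 51 is chosen, the largest possible trial is one patient smaller than the text now states. No procedure or analysis changes.

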### **8.1 Enrollment**

Approximately 60 adult male or female kidney transplant recipients will be enrolled at Vanderbilt University Medical center.

Patients who are willing to participate in the study and who have given written informed consent may be screened up to 7 days prior to enrollment. Screening procedures are detailed in [Section 10.1.1](#).

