## **14.7 Interim Analysis**

An interim analysis will be conducted when cognitive data are available for 17 evaluable patients who have completed Visit 3. An estimate of the variation and effect of ENVARSUS XR for CPT-III omission measures will be calculated. A sample size adjustment may be made according to the algorithm described in [Section 14.1](#). Given the exploratory nature of the study, the final analyses described above will not be adjusted for this additional look. The inflation of type I error is minimum ( $\sim 0.005$ ).

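### Section 14.1 gives two final sample sizes that do not agree (about 60 enrolled, or 34 to 52 evaluable set by the interim), and nothing says which one governs

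*Combined protocol and SAP*

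**What the plan says.** - Enrolment is stated without reference to the interim. Section 8.1: "Approximately 60 adult male or female kidney transplant recipients will be enrolled". The synopsis (Sample Size Considerations) and 14.1: "The study aims to enroll approximately 60 patients". Section 6.1 repeats the figure.
- Section 14.1 expects 10–15% drop-out and at most 52 evaluable patients, and uses this as reassurance about power: "We simply need at least 34 patients to have adequate power, but we anticipate approximately having 52".
- The same section takes 34 as the planned size and re-estimates it at 17 evaluable patients from the observed change and its variation. The result is called the final sample size and is limited to 34–52. At the lower end, "the sample size remains at 34 if the adjusted estimate is below 34". At the upper end the multiplier is r = 1.5, said to give 52.
- Section 14.7: "A sample size adjustment may be made according to the algorithm described in" section 14.1. It bases the estimate on CPT-III omission measures, leaves the final analysis unadjusted and puts the type I inflation at about 0.005.
- Section 14.2 defines the ITT set as all enrolled patients. Section 14.5.1 runs the primary analysis on both the ITT and Evaluable sets.

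**The concern.** A plan that will enrol 60 regardless and a plan that stops at 34 when the interim looks favourable are different trials. If 60 are enrolled and drop-out is the only loss, the expected yield already meets the upper limit of the rule, so there is nothing to adjust. If the rule is followed and returns 34, recruitment could end about 20 short of the stated enrolment.

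Because 14.7 words the adjustment as optional, the text lets the choice be settled after an effect estimate has been seen, in an open-label single-centre study. At stake are the number of patients in the primary paired test, the power that can be claimed and, to a lesser degree, the false-positive rate.

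**Working it through.** **Inputs.** Section 14.1: "In order to detect an effect size of 0.5", "with 80% power and a one-sided type I error rate of 0.025", 34 evaluable, interim at 17, r = 1.5, drop-out 10–15%, enrolment about 60. Synopsis, Analysis Methods: the change is "evaluated using paired t-test at 0.05 significance level", read here as two-sided 0.05, which corresponds to one-sided 0.025.

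**1. The plan's own figure.** For a paired t-test, power = P(T > t₀.₉₇₅,ₙ₋₁), where T is noncentral t with n − 1 degrees of freedom and noncentrality 0.5√n. This gives 0.795 at n = 33 and 0.808 at n = 34, so 34 is reproduced. At n = 52 power is 0.943. At an effect size of 0.4 it is 0.62 (n = 34) and 0.81 (n = 52).

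**2. Enrolment each size needs.**
- 34 evaluable: 34/0.90 = 37.8, so 38; 34/0.85 = 40.
- 60 enrolled: 60 × 0.85 = 51; 60 × 0.90 = 54.

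The two statements differ by 20–22 enrolled patients, or up to 52 − 34 = 18 evaluable.

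**3. Internal figures.** r × n = 1.5 × 34 = 51, not 52. At 10% drop-out 60 enrolled yield 54, so 52 is not the maximum either.

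**4. What the rule would deliver.** Simulated on normal changes, assuming the interim uses the primary outcome. N = ((1.960 + 0.842)/observed standardised change at 17)², limited to 34 at the bottom and 51 or 52 at the top, with the upper limit used when the interim effect is in the wrong direction. The final test is one unadjusted t-test. At effect size 0.5:

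| Size rule | Mean N | Share at 34 | Power |
|---|---|---|---|
| Fixed 34 | 34 | – | 0.81 |
| Interim rule | about 41 | 52–54% | 0.91–0.92 |
| Fixed 52 | 52 | – | 0.94 |

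The ranges cover the cap (51 or 52) and whether two patients are added to N for the t distribution. The rule reaches its upper limit in about a third of trials, so about 52 evaluable is not what it delivers.

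**5. Type I error (two-sided, 0.050 for a fixed size).**
- Rule followed: about 0.053. If an interim effect in the wrong direction is treated like one in the right direction, about 0.056.
- 34 or 52 chosen once after the interim to maximise the chance of rejection, then one test: at most about 0.058 (one-sided about 0.029).
- For comparison, 0.05 + 0.005 = 0.055 if the stated inflation is two-sided; 0.025 + 0.005 = 0.030 if it is one-sided.

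**6. Patients beyond the interim-set size.** The interim needs 17 evaluable patients past Visit 3 at Month 4. At 10–15% drop-out, 17 evaluable means 19–20 enrolled. The plan gives no accrual rate. If it were (40 − 20)/4 = 5 per month, the 40 patients needed for a size of 34 would already be enrolled when the interim data arrive (ignoring visit windows and delay in starting the drug). Under 14.2, any beyond that enter the ITT analysis.

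**The case against.** The best defence is that 60 is a recruitment target chosen so that the rule's upper limit can be supplied, and that the optional wording in 14.7 only means the algorithm may or may not ask for more than 34. That reading is coherent, but it is not written down. The note in 14.1 anticipating 52 evaluable speaks against it, and no sentence closes enrolment at the interim-set size.

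Three parts of the defence stand:
- The study is declared exploratory, and at effect size 0.5 power is at least 0.81 on every reading that reaches 34 analysed patients. The conflict does not by itself leave the trial underpowered for its own target.
- Drop-out is not the only loss. The Evaluable set also excludes patients with a trough outside 3–9 ng/mL, so 60 enrolled may yield fewer than 51–54 and the rule is not certain to be redundant.
- The simulation assumes an interim on the primary outcome. As written, the rule uses CPT-III omission, which is neither the primary endpoint nor on the Schedule of Study Activities. With a weakly correlated interim measure, the rule's own inflation falls towards zero. The disagreement over size and power remains.

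A reader might infer a serious false-positive problem, with the final test run at two sample sizes and the better result reported. The documents do not support that: they describe one final test and no efficacy test at the interim.

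**Conclusion.** The plan does not define its final sample size. Two statements in one section lead to 38–40 or about 60 enrolled, and at effect size 0.5 to power of 0.81 or 0.94. The reassurance about power rests on 52 evaluable patients, whereas the rule, if run on the primary outcome, would stop at 34 in about half of trials. The 51-versus-52 and 52-versus-54 discrepancies are small but need correcting.

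The type I effect is minor. Followed as stated, the rule is broadly consistent with the plan's figure of about 0.005. The worst single choice after the interim exceeds a two-sided reading of that figure by about 0.003 and stays within a one-sided reading.

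It would also be too strong to say that the documents commit to 60 whatever the interim shows. They state 60 without a condition and leave open how it relates to the rule.

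These results assume normal changes, effect size in units of the SD of change, and an interim on the primary endpoint. The point should be settled before the interim, but in an exploratory study it does not threaten the design as a whole.

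**What to change.** State one rule before any interim data are seen.

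**Simplest option.** Enrol the planned 60 and analyse the primary paired score once on all patients who have it. Delete the effect-based sample-size adjustment and the type I inflation sentence (synopsis, Sample Size Considerations and Interim Analysis; 14.1; 14.7). State power by number evaluable (0.81 at 34, 0.94 at 52, for effect size 0.5), and note that trough exclusions may bring the Evaluable set below 52.

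**If the adjustment is kept.** Make the interim-set size binding, name 60 as a ceiling, correct the cap to 51 or change r, and state how patients beyond that size are analysed. The interim variable must also be reconciled with the primary endpoint and the schedule.

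**Cost.** Either option is a wording amendment with no patients beyond the 60 already planned. The first gives up the chance of finishing at 34.
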